4.3 Accountability Procedures for Study Vaccines

It is the responsibility of the Investigator to delegate the supervision for accurate monitoring of the receipt, storage, dispensing and accounting of all study material according to accepted industry practice. Sites must maintain and retain accurate, original site records of study material inventory as well as copies of all invoices of study material shipments and records of study material distribution.

Drug accountability information will be collected for tracking study vaccines (eg, date material was received, dispensed to individual subjects, and amount used and unused on site etc.).

Each site must keep all used and unused study material until the Clinical Research Associate (CRA) has performed vaccine accountability and arranges return to the central depot vendor or gives instruction for used vaccine disposal. Expired vaccine should be separately quarantined until CRA has completed accountability monitoring.

Shipment of vaccine will be contingent on enrollment at the study sites. Detailed instructions on packaging, preparation, administration, and accountability are found in the VAX24-102 Pharmacy Manual.

5 STUDY PROCEDURES

Source documents and source data should meet the elements of data quality and integrity (ALCOA-C: attributable, legible, contemporaneous, original, accurate, and complete).

5.1 Informed Consent

The Investigator must obtain informed consent from study subjects at the Screening/Baseline visit prior to starting any study-related activities. All prospective subjects must sign and date an Institutional Review Board (IRB)-approved ICF. For further details on informed consent, refer to [Section 10.3](#).

5.2 Subject Number Assignment at Screening

Screening procedures are listed in the Schedule of Events ([APPENDIX A](#)).

Each subject who signs an ICF will receive a sequential three-digit identification number unique to the site (eg, 001, 002...). When screening information is subsequently entered into the EDC, each subject will be assigned a subject identification number with the following format:

VAX24-102 - two-digit site number - three-digit identification number

An example of a subject identification number is: VAX24-102-01-001. Subject numbers will be sequential since screen-failed subjects will be entered into the EDC system.

Each site is required to record the reason(s) for screen failure for all subjects who receive a subject identification number within the EDC system. Sites may elect to use a pre-screening consent form and maintain a pre-screening log for those subjects contacted for the study and will provide that log to the Sponsor or designee upon request.

Re-screening

A subject who meets exclusion criterion of having a current acute febrile illness at the time of scheduled enrollment may be re-screened after resolution of the acute illness. A subject who meets exclusion criteria of taking an investigational product, licensed vaccines, or medications (i.e., systemic corticosteroid) within 30 days (or blood or blood product within 90 days) prior to Day 1 may be re-screened after the appropriate duration has passed. If an eligible subject is not able to be randomized and treated within 30 days of the Screening period, all Screening/Baseline procedures must be conducted again, including re-consenting and use of a new subject ID number. A subject may be re-screened one time only. Re-screening is not otherwise permitted.

If a subject is re-screened, a new subject number will be assigned as they are entered into EDC for a new Screening/Baseline visit and the previous subject number will be captured in the source file of the newly assigned subject number.

5.3 Medical History

Medical history information will be collected from subjects at the Screening/Baseline Visit. Medical history will include (but not be limited to) demographic information, current and past medical conditions, and prior and concomitant medications taken within 30 days prior to Day 1, including history of vaccinations. At the investigator's discretion, all significant and relevant medical history from birth should be captured in eCRF.

In consideration of the availability of commercial pneumococcal vaccines and ongoing investigational vaccine clinical research, the history of pneumococcal vaccination must be collected and, if the subject's medical records and/or state-mandated vaccine registry are available, the site is required to maintain this documentation as part of the eligibility review.

5.4 Physical Examination

A complete physical examination will be performed on subjects during the Screening/Baseline visit.

The examination should include:

- Height
- Body weight
- Vital signs
- General appearance
- Eyes-ears-nose-throat
- Head-neck
- Lungs-chest
- Heart
- Abdomen
- Musculoskeletal
- Lymph nodes
- Skin
- Extremities
- Neurological

A physical exam may be performed on subjects at additional time points if indicated by AE reporting.

5.5 Vital Signs

Vital signs collected from subjects will include blood pressure, heart rate, respiratory rate, and oral temperature. The first set of Screening/Baseline vitals are to be collected for inclusion of the subject into the study. Repeat measurements on abnormal vital parameters are allowed one additional time for inclusion into the study. After Day 1, abnormal vital signs can be repeated for confirmation of clinical significance. Vital signs should be taken after at least 5 minutes in supine position.

5.6 Laboratory Tests

5.6.1 Blood Volume

Samples for immunogenicity are collected by venipuncture, in the appropriate blood container tubes according to the schedule of sample collection shown in [APPENDIX A](#). The maximum volume of blood taken from a subject is up to ~34 mL. Phlebotomy will observe the American Red Cross limit of no more than 450 mL in any 8-week period.

Table 4 Blood Collections

Study Day	Blood volume (mL)	Laboratory Tests	Tube Type/volume	Minimum # of 2 mL cryovials
Day 1	17	Immunogenicity	2 SST 8.5 mL	8
Day 29	17	Immunogenicity	2 SST 8.5 mL	8

NOTE: ALL CRYOVIALS SHOULD BE FROZEN AND STORED AT -20° C OR COLDER AND SHIPPED ON DRY ICE.

To minimize the impact of lost or damaged shipments, the frozen serum samples will be sent in separate consignments (primary, backup) to the central laboratory.

Further details regarding specimen collection, processing, and shipping will be provided in the Central Laboratory Manual.

5.6.2 Immune Response Assessments

Serum antibody responses to pneumococcal polysaccharides induced by vaccination will be measured using 2 standard assays, OPA and multiplexed Meso Scale Discovery (MSD) IgG.

The OPA assay has been developed and qualified by Nexelis, a GCP-compliant central laboratory, to analyze the 24 polysaccharide antigens contained in VAX-24. The OPA assay has been consistently used as the method for measuring the functional capacity of pneumococcal antibodies, as antibodies to pneumococcal PS protect the host by opsonizing pneumococci (marking pneumococci for destruction) for phagocytosis ([Burton and Nahm 2012](#)).

The MSD assay has been developed and qualified by Nexelis to measure IgG responses against the 24 polysaccharide antigens contained in VAX-24. The MSD multiplex electrochemiluminescent assay is an immunoassay platform that allows simultaneous measurement of responses against multiple antigens and has been used to evaluate responses to various pneumococcal conjugate vaccines ([Marchese 2009](#), [Goldblatt 2011](#), [Feysaguet 2019](#), and [Nolan 2020](#)).

The immune responses (as assessed by OPA and IgG assays) against the 20 polysaccharide antigens common to PCV20 and VAX-24 (1, 3, 4, 5, 6A, 6B, 7F, 8, 9V, 10A, 11A, 12F, 14, 15B, 18C, 19A, 19F, 22F, 23F and 33F) will be compared in the various treatment groups (VAX-24 at 3 different dose levels, and the comparator vaccine), and the 4 incremental polysaccharide antigens contained in VAX-24 (2, 9N, 17F and 20B) will be evaluated separately.

5.7 Randomization

Randomization will be 1:1:1:1 for the four treatment groups. The randomization code will be generated using a permuted block algorithm. The randomization with treatment assignment for each subject will be generated in IBM EDC by the designated blinded personnel user.

Subject eligibility will be confirmed and documented by the Investigator immediately prior to randomization of each subject. After the subject is randomized, both the unblinded and blinded personnel will be able to view the blinded randomization information under the Patient List tab. However, only the unblinded personnel will be able to view the treatment arm assigned by randomization for specific subjects. Additional details for this process are provided in the Pharmacy Manual.

A subject will be considered enrolled once a randomization number has been assigned within the EDC system. The study will be conducted as an observer-blind study. Neither subjects, clinical site evaluators including the investigators, nor the Sponsor will know subjects' individual

treatment assignments until all subjects have completed their participation in the study and the database has been cleaned and locked.

The following safeguards will be employed to reduce the risk of inadvertent unblinding:

- Each clinical site is required to have a blinding plan that outlines its process on blinding the subject in situations such as administration of IM injection with different syringe types, transfer of study vaccine to the clinic room for administration, providing initial training and reminders to the subjects to not disclose their experiences with the injection except with unblinded study staff.
- No Sponsor personnel other than the designated unblinded monitor(s) and third-party unblinded biostatistics and programming staff will have access to the randomization treatment assignments.
- Should any subject or blinded staff member become inadvertently unblinded, the Investigator will promptly (within 24 hours of the Investigator's awareness of the error) disclose the event to the Sponsor clinical study manager and medical monitor in a blinded fashion (disclosing only subject number, not treatment) so that corrective action can be initiated. The unblinding sequence of events will be documented as a protocol deviation and retained as source documents. See [Section 5.14](#) for details on Emergency Unblinding.

5.8 Study Vaccine Administration

Immediately prior to study vaccine administration, staff should recheck subject eligibility. Once these procedures are performed, study vaccine can be administered. As a reminder, VAX-24 is to be shaken vigorously immediately prior to administration to obtain a homogenous, white suspension in the syringe and administered within 60 minutes from time out of refrigerator. All doses of study vaccine are 0.5 mL in volume and are administered by IM injection with a Sponsor-provided 1 mL syringe and 25 gauge 1" (or 1.5", at the Investigator's discretion) needle as described above or PCV20 PFS, using universal precautions and sterile technique. Injections will be administered into the deltoid muscle by an unblinded staff member delegated by the Investigator.

5.9 Acute Observation

The subject will be monitored by blinded study staff for signs of an acute adverse reaction and vital signs will be obtained at least 30 minutes after injection. If a subject reports any symptom collected as solicited AEs for this study, the blinded study staff will advise them to record the details in their diary at the end of their day.

Allergic reactions to the study vaccine are possible; therefore, appropriate drugs and medical equipment to treat acute anaphylactic reactions must be immediately available and a medically

qualified study team member trained to recognize and treat anaphylaxis must be present in the clinic during the entire post-dosing monitoring period.

5.10 Solicited Adverse Events

Solicited AEs will be collected for 7 days, after the injection, starting on Day 1. Solicited AEs for this study are local events of pain, erythema (redness) and edema (swelling) at the injection site, and systemic events of oral temperature $\geq 100.4^{\circ}\text{F}$, fatigue, headache, muscle pain, and joint pain.

Subjects will receive and be trained on the use of a paper diary to observe, measure, and record these solicited AEs. The diary will serve as the primary source document and data will be entered by the site into the subject visit solicited AE form in the EDC system. A digital thermometer will be provided to the subject to measure oral temperature each day, and it is to be recorded daily in the diary. To record injection site local reaction, a ruler will be provided to the subject to measure the diameter of redness and swelling at the largest point of the reaction each day; it is to be recorded daily in the diary.

Subject is to be instructed to immediately call the study site if they experience a grade 3 (severe) or grade 4 (life threatening) symptom. Study site will determine if the subject needs to return to the site for safety evaluation and follow-up.

Study staff will review the signs and symptoms recorded in the diary and the action taken for the event during the subject's next scheduled clinic visit (Day 8). The Investigator will assess all recorded solicited events for severity and relatedness during this subject visit. Severity will be graded according to the FDA Toxicity Grading Scale (FDA 2007). The results of the Investigator's assessment, if different from the subject's entry, will be recorded in a separate field specified for Investigators within the EDC system.

Symptoms continuing beyond the solicited AE collection period (7 days following the injection) will be collected and recorded as an unsolicited AE in the source document.

5.11 Unsolicited Adverse Events

Unsolicited AEs (any AEs not listed in the diary) will be collected for this study. Details regarding definitions, evaluation, reporting periods, and documentation are outlined in [Section 7](#).

5.12 Prior and Concomitant Medications and Procedures

At the Screening/Baseline visit, the details of prior and concomitant medications and procedures (through 30 days prior to Day 1) usage will be collected, including history of vaccinations. From Day 1 through Day 29, the details of all concomitant medications and procedures including those associated with solicited AEs and unsolicited AEs will be collected.

Concomitant medications and procedures associated with an SAE, NOCI, or MAAE will be collected through the end of the study.

5.13 Prohibited Medications and Therapies

Subjects must not have received or be planning to receive:

- Licensed or investigational pneumococcal (pneumonia) vaccine.
- Investigational agents or study product from 30 days prior to Day 1 through the duration of the study.
- Other (non-pneumococcal) licensed vaccines from 30 days prior to Day 1 through Day 29.
- Blood or blood product (including IGIV) from 90 days prior to Day 1 through the duration of the study.
- Systemic immunosuppressant therapy (eg, chemotherapeutics) and immunostimulants.
- Immunomodulatory medications (eg, oral corticosteroids) from 30 days prior to Day 1 or received systemic corticosteroids exceeding physiologic replacement doses within 14 days prior to study vaccination through Day 29.

The history of all prohibited medications at any time during study participation (regardless of association with an AE) will be collected.

5.14 Emergency Unblinding

The Investigator may obtain a treatment assignment for a study subject only in the case of a medical emergency in which knowledge of the treatment is necessary for the management of an AE. Emergency unblinding procedures is to be conducted in the IBM EDC system. In rare cases of technical issues with the EDC system, the Investigator or designee can request this information via the Emergency Unblinding Request Form through the Vaxcyte Clinical Trial Manager or Medical Monitor. The Investigator must notify the Medical Monitor (and as backup, Medical Director) no later than 24 hours following Unblinding. Additional details for this unblinding process are provided in the Pharmacy Manual.

5.15 Protocol Deviations

The Investigator and delegated staff are responsible for conducting the study in accordance with the protocol. Any deviation from the protocol must be documented in the study file. In addition, deviations must be reported to the IRB as applicable. Subject-specific deviations must be recorded in the subject's source documents. The Sponsor will review all protocol deviations on an ongoing basis and will be responsible for categorizing protocol deviations.

5.16 Dosing Errors

The Investigator or designee must report any error in the dosing of study vaccine to the site-assigned unblinded CRA and Medical Monitor or designee within 24 hours of the Investigator's awareness of the error. Additional information regarding the dosing error may be provided as a follow-up report. A dosing error without signs or symptoms is not considered an AE and should be documented as a protocol deviation and investigated further.

5.17 Study Completion: For Individual Subjects

A subject is considered to complete study participation after completion of the Month 6 Phone Call and completion of any required safety follow-up.

5.18 Early Discontinuation

An individual subject is considered to undergo Early Discontinuation if the subject stops study participation before the Month 6 Phone Call.

An enrolled subject may voluntarily withdraw consent for further participation at any time before the Month 6 Phone Call. The Investigator will request (but cannot require) such subjects to provide the reason(s) for withdrawal of consent and to undergo an Early Discontinuation visit.

In addition, the Investigator, at his or her discretion, may withdraw a subject from further participation in the study. Criteria for withdrawal by the Investigator include:

- Noncompliance with the protocol
- Lost to follow-up – requires documentation of at least 3 unsuccessful attempts to contact the subject. Lost to follow-up will be determined after the date of the subject's projected last visit. Final attempt should be accompanied with a certified mail.
- Other reason(s) which, in the opinion of the Investigator, indicates that continued participation in the study is not in the best interest of the subject.

The Investigator or designee must report any early discontinuation for safety reasons to the Medical Monitor or designee within 24 hours of discontinuation. Additional information regarding ongoing AEs may be provided as a follow-up report.

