
Study Design
 
This Phase 2, randomized, observer-blind study is to be conducted in healthy adults aged 65 and older. Subjects may screen for up to 30 days prior to randomization; however, they may be screened and randomized within the same visit. Demographics, medical history, and concomitant medication use will be collected. Subjects will be randomly assigned in a 1:1:1:1 ratio to receive either VAX-24 at one of three dose levels or the active comparator, Prevnar 20 (PCV20).
 
Subjects will receive VAX-24 or PCV20 on Day 1. Solicited AEs will be collected for 7 days post-vaccination via diary and unsolicited safety information for 28 days post-vaccination, with SAEs, new onset of chronic illnesses (NOCIs), and medically attended adverse events (MAAEs) collected up to 6 months post-vaccination. All subjects will have blood samples drawn for immunogenicity analysis (OPA and IgG) at Days 1 and 29. A Data Monitoring Committee (DMC) will be adjudicated for the study. If the study meets a pre-defined stopping criterion, the study will be paused, and data reviewed by the DMC prior to re-starting the enrollment.

Study Population
 
The study population will be composed of at least 200 healthy US adults 65 years and older.

Main Criteria for Eligibility
 
Healthy adult volunteers aged 65 and older, without previous history of pneumococcal disease or previous receipt of a licensed or investigational pneumococcal vaccine.

Test Product; Dose; and Mode of Administration
 
VAX-24 will be administered once, by intramuscular (IM) injection, at one of 3 dose levels: 1.1, 2.2, or 2.2/4.4 mcg/dose, where mcg is the measured amount of total polysaccharide per serotype.

Reference Therapy; Dose; and Mode of Administration
 
PCV20 will be administered once, by IM injection, at a dose of 0.5 mL, as packaged by the manufacturer.

Treatment and Duration of Treatment

Treatment consists of a single IM injection of VAX-24 or a single IM injection of PCV20.

Safety Assessments

Subjects will be evaluated for unsolicited and solicited adverse events (AEs), including injection site and systemic reactions following vaccine administration. Additionally, changes in NOCI, physical examinations, and vital signs following administration of study vaccines will be evaluated.

Statistical Methods

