2 OBJECTIVES AND ENDPOINTS

2.1 Primary

The primary objective is:

- To evaluate the safety and tolerability of a single injection of VAX-24 at three dose levels administered to healthy adults 65 years and older.

Safety and tolerability will be assessed by measuring the incidence of solicited local and systemic adverse events (AEs), unsolicited AEs, serious adverse events (SAEs), new onset of chronic illness (NOCI), and medically attended adverse events (MAAEs):

- Percentage of subjects reporting solicited local reactions within 7 days after vaccination (redness, swelling, and pain at injection site).
- Percentage of subjects reporting solicited systemic events within 7 days after vaccination (fever, headache, fatigue, muscle pain, and joint pain).
- Percentage of subjects reporting unsolicited AEs within 1 month after vaccination.
- Percentage of subjects reporting SAEs and NOCI within 6 months after vaccination.
- Percentage of subjects reporting AEs with a new onset or a worsening of a condition that prompts the subject to seek unplanned medical advice at a physician's office, urgent care center, or Emergency Department

[figure not shown]

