5.19 Subject Replacement

Subjects who undergo Early Discontinuation after randomization and before vaccine administration may be replaced by randomizing an additional subject at the Sponsor's discretion. Subjects who undergo Early Discontinuation after study vaccination will not be replaced.

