7.5.1 Reporting Periods

The four reporting periods for solicited AEs begin immediately after study vaccine administration and continue for 7 days after the injection. The reporting period for unsolicited AEs is immediately after study vaccine administration on Day 1, continuing through Day 29. AEs that correspond to solicited AE terms but occur outside of (or continue past) the solicited AE collection periods are also collected through the unsolicited AE reporting periods. The reporting period for SAEs begins at the time of informed consent and continues for the duration of study participation.

A summary of the reporting periods is presented in Figure 2.

Figure 2 Safety Events Reporting Periods

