6.1.6. Missing, Unused, and Spurious Data

Binary endpoints / Continuous data:

Missing data are assumed to be missing at random and ignorable. Missing data will not be estimated or imputed. Denominators for percentages will be based only on the number of subjects with non-missing values. The only exception is:

- Systemic Solicited AEs with missing "Relationship to study vaccine" will be analyzed as "Possibly related".

Dates:

For partial or missing AE start dates the following imputation rules will be applied:

1. If year is not missing and is after the year of first dose:
 - a. If month is missing, then month will be imputed as January.
 - b. If day is missing, then day will be imputed as the first of the month.
2. If year is not missing and is the same as the year of the first dose:
 - a. If month is missing, then impute the month as the month of the first dose date.
 - b. If day is missing, and the month is the same as the month of the first dose date, then impute day as the day of the first dose date.
 - c. If day is missing but month is after the month of first dose date, then impute day as the first day of the month.
3. If year is missing, then impute the year as the year of the first dose date:
 - a. If month is missing, then impute the month as the month of the first dose date.
 - b. If day is missing, then impute the day as the day of the first dose date.
4. If the start date is completely missing, but the AE is either ongoing (i.e. AE stop date is missing) or the stop date is after the first dose date then impute the start date as the first dose date.
5. For any cases involving the rules above, if the AE end date is before the AE start date, then do not impute the AE start date and assume that the AE is treatment emergent/concomitant for the purpose of the analysis. Further, if the AE stop date occurs prior to the first dose date, do not impute the AE start date, and assume that the AE is not treatment emergent.

No imputations will be applied to AE stop dates or other dates. As indicated above, AEs with missing stop date are considered ongoing.

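### Protocol 5.18 allows a vaccinated subject to be withdrawn for noncompliance, which in a single-injection trial ends only data collection, including 6-month safety follow-up that serves three of the six primary endpoints

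*Protocol*

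**What the plan says.** **Withdrawal rule.** Protocol 5.18 gives the Investigator a discretionary power: "In addition, the Investigator, at his or her discretion, may withdraw a subject from further participation in the study". The first criterion listed is "Noncompliance with the protocol", with no qualifier of severity or timing. The rule reaches vaccinated subjects, because "An individual subject is considered to undergo Early Discontinuation if the subject stops study participation before the Month 6 Phone Call", and Protocol 5.19 expects such cases: "Subjects who undergo Early Discontinuation after study vaccination will not be replaced".

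**Treatment.** The Protocol Synopsis states: "Treatment consists of a single IM injection of VAX-24 or a single IM injection of PCV20".

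**Endpoints.** Protocol 2.1 includes among the primary safety endpoints: "Percentage of subjects reporting SAEs and NOCI within 6 months after vaccination". SAP 3.2 lists six primary endpoints. Solicited local and solicited systemic events run to 7 days and unsolicited AEs to 1 month. SAEs, NOCIs and MAAEs run to 6 months.

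**Collection after withdrawal.** Protocol 7.5.1 ties SAE reporting to participation: "The reporting period for SAEs begins at the time of informed consent and continues for the duration of study participation". After Day 29, NOCIs and MAAEs are gathered through the Month 3 and Month 6 calls (Protocol 6.1.5). No clause keeps a withdrawn subject in those calls.

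**Analysis.** SAP 4.1 keeps every exposed subject in the Safety Population except those lost at Day 1 with no AE reported. SAP 6.1.6 adds: "Missing data are assumed to be missing at random and ignorable".

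**The concern.** In a trial with repeated dosing, withdrawing a noncompliant subject may at least stop further exposure. Here nothing is left to stop after Day 1. What ends is the observation that the primary objective, safety, depends on.

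Withdrawal is not needed to protect the immunogenicity analysis either. Protocol 9.3 and SAP 4.1 and 4.2 already exclude from the IEP subjects who took a prohibited product, had an out-of-window sample or had another major deviation.

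The possible harm is a 6-month SAE, NOCI or MAAE percentage that is too low. The subject was exposed and counts in the denominator, but nobody asks about new events after the withdrawal date. Because the withdrawal is discretionary, there is no assurance that the loss is unrelated to the subject's health, which is what the SAP's missing-data assumption requires.

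**Working it through.** **1. What a withdrawal cuts, by timing**

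| Withdrawal | Data lost |
|---|---|
| Before the diary ends | Rest of the 7-day diary, 1-month AEs, Day 29 serum, 6-month SAE/NOCI/MAAE |
| After the diary, before Day 29 | Rest of the 1-month AEs, Day 29 serum, 6-month SAE/NOCI/MAAE |
| After Day 29 | 6-month SAE/NOCI/MAAE only |

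Serum drawn at an Early Discontinuation visit before Day 26 does not replace the Day 29 sample in the IEP, whose window is Day 26 to Day 34 (Protocol 9.3).

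**2. Share of the 6-month window lost**

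Input: Month 6 is 180 days after Day 1 (Protocol 6.1.5). This agrees with the 211-day maximum in Protocol 3.3: 30 + 1 + 180 = 211. For withdrawal on Day d, share lost = (180 − (d − 1)) / 180.

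- Day 8: 173/180 = 96%
- Day 29: 152/180 = 84%
- Day 90: 91/180 = 51%

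**3. What the safeguards recover**

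- Protocol 6.2 requests one Early Discontinuation visit. Procedures are listed for a visit within 7 days and for one after Day 8 and before Day 29. None are listed after Day 29, and neither list names NOCI or MAAE.
- Protocol 7.4 requires AEs to be followed to resolution or stabilisation. That covers events already known and does not look for new ones.

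**4. How the subject is counted**

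SAP 6.4 produces all safety summaries on the Safety Population. For solicited AEs, SAP 6.4.1.1 restricts each summary to subjects with at least one observation. SAP 6.4.1.2 has no such rule for SAEs, NOCIs or MAAEs. SAP 6.1.6 bases denominators on non-missing values, but the absence of an AE record is not ordinarily a missing value. A subject withdrawn on Day 29 with no event can therefore stay in the denominator as event-free. SAP 5.4, the section on withdrawals, covers only replacement.

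**5. Size in one arm**

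Input: 200/4 = 50 per arm (SAP 2.3). The documents give no withdrawal rate and no event rate, so the rest is assumption.

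- One missed first event: 1/50 = 2 points.
- Upper limit, assuming 1 to 3 subjects per arm are withdrawn and every one has a later unrecorded first event: 1/50 to 3/50 = 2 to 6 points.
- Expected understatement = w × q / 50, with w withdrawn and q the chance of a later first event. For an assumed q of 5% to 20%: w = 1 gives 0.1 to 0.4 points, and w = 3 gives 0.3 to 1.2 points.
- Illustration at an assumed 10% withdrawal (5 of 50) with 2 observed events: 2/50 = 4.0% on all exposed, 2/45 = 4.4% on completers, and (2 + 5)/50 = 14% if every withdrawn subject had an event.

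**6. Precision**

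The one-sided 95% upper bound with zero events is 1 − 0.05^(1/n): 5.8% for n = 50 and 6.4% for n = 45. The chance of seeing at least one event at a true 2% rate is 1 − 0.98^n: 63.6% and 59.7%. The loss of precision is small, so the issue is possible bias.

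**The case against.** The strongest reply is that the gap is narrow and the protocol otherwise leans towards retention.

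- Section 5.18 is permissive. A reader might infer that sites are told to withdraw anyone who misses a visit or takes a prohibited product, but no passage says so. Protocol 5.13 collects prohibited medications throughout participation and 6.1.5 reviews them at the Month 3 and 6 calls, so such subjects are expected to be in follow-up still. This stands. It also means that the 5.18 ground sits awkwardly with the rest of the protocol.
- A reader might infer that an illness leading to a prohibited product is lost when the subject is withdrawn. That illness normally comes first and is already reportable, and a subject with a recorded MAAE still counts for that endpoint. Only a later first event of a type not yet recorded is lost. This stands, and it weakens the argument that the missingness depends on outcome.
- Safeguards exist: the 6.2 visit, the 7.4 follow-up, 24-hour reporting of discontinuations for safety reasons, and a rule that loss to follow-up is declared only after the projected last visit. They reduce the loss but do not keep surveillance for new events open. The last one shows an inconsistency: a subject who cannot be reached stays open to the end, while one who can be reached but is noncompliant may be dropped at once.
- Investigators and assessors are blinded (Protocol 4.2 and 5.7), so withdrawal should not depend on the known arm. This stands. The documents do not support a claim of a biased comparison between arms, and they give no evidence on variation between sites.

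**Conclusion.** The point holds as a limited weakness. Protocol 5.18 permits withdrawal of a vaccinated subject for noncompliance. That withdrawal ends only data collection, and nothing in the documents restores surveillance for new SAEs, NOCIs and MAAEs to Month 6. The affected percentages can be understated within an arm.

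Two stronger readings are not supported. The first is that withdrawal costs nothing but the 6-month follow-up and that this follow-up makes up the primary endpoints. The cost is confined to that follow-up only after Day 29, and three of the six primary endpoints in SAP 3.2 are complete by 7 days or 1 month. The second is to take 2 to 6 points as an estimate. It is a ceiling that assumes 1 to 3 withdrawals per arm and a missed first event in every one. With an assumed 5% to 20% chance of such an event, the expected understatement is about 0.1 to 1.2 points.

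The true size is unknown because the documents give no withdrawal rate. The change is justified mainly because the rule discards primary safety data for no analytical gain and is cheap to correct.

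**What to change.** - **Protocol 5.18.** State that after vaccination, noncompliance (missed visits or procedures, or use of a prohibited product) is recorded as a protocol deviation, handled by IEP exclusion under SAP 4.2, and is not by itself a ground for ending safety follow-up. Such subjects stay in the Month 3 and Month 6 safety calls unless they withdraw consent. Withdrawal of consent and the ground concerning the subject's best interest are left as they are.
- **Protocol 6.2.** Add a review of SAEs, NOCIs and MAAEs for discontinuation after Day 29, where no procedures are listed now.

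The cost is a short amendment and a reminder to sites. The calls are already scheduled for every subject. The downside is a few extra call attempts to poorly compliant subjects.
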